2.2.1 Subgroup of interest

2.3 Patient disposition, demographics and other baseline characteristics

2.3.1 Patient disposition

The number of screened and screen failure subjects will be shown for all subjects (total). The reason for screen failure will be summarized.

The number of subjects in each analysis set will be presented for each treatment group and all subjects (total). The reason for excluded/excluding from any analysis set will be listed.

The number and percentage of complete Week 4 visits, Week 12 (EOT) visits, Week 16 (EOS) visits or early discontinued from treatment/study will be presented by treatment groups and all patients (total) based on Randomized Set.

The number and percentage of patients who have experienced protocol deviations (PD) will be tabulated by deviation category, treatment groups and all patients (total). The summary of overall important PDs (including COVID-19 related PDs), important PDs excluding COVID-19 related PDs, and COVID-19 related PDs will be provided.

2.3.2 Demographic and baseline characteristics

Demographics and baseline characteristics will be summarized using the randomized set, including disease characteristics, prior and background medications to treat urticaria, and relevant medical histories.

Summary statistics will be presented for continuous demographic and baseline characteristic variables for each treatment group and all patients (total).

Continuous variables:

- Age (years)
- Height (cm)
- Weight (kg)
- Body mass index (BMI) = (body weight in kilograms) / (height in meters)²
- Baseline UAS7 score
- Baseline AAS7 score
- Baseline DLQI score
- Time since diagnosis of urticaria = (inform consent date – diagnosis date + 1)/365.25

The number and percentage of subjects in each category will be presented for categorical variables for each treatment group and all patients (total).

Categorical variables:

- Age categories (< 65, >= 65-<85years , >=85 years)
- Gender

- Race
- Ethnicity
- BMI groups (< 25, 25 -<30, >= 30 kg/m²m²)
- Baseline UAS7 (Mild disease: UAS7 6-<16; Moderate disease: UAS7 16-<28; Severe disease UAS7 28-42)
- Baseline AAS7 = 0 response (Yes, No)
- Previous exposure to anti-IgE therapy (Yes, No)
- Geographic region (Japan, US, LaCAN, RE)
- Previous experience of Angioedema (Yes, No)
- Baseline CU-index (Positive, Negative)
- Baseline total IgE level (High, Low) (the median value of all patients at each analysis will be used as threshold)

2.3.3 Medical history

Any significant prior or current medical condition at the time of signing informed consent will be coded using the MedDRA dictionary.

Non-urticaria related medical conditions will be summarized by primary system organ class and preferred term.

The urticaria related medical history will be summarized separately.

Cardiovascular history and family malignancy history will be listed if needed.

2.4 Treatments (study treatment, rescue medication, concomitant therapies, compliance)

The analysis of study treatment data will be based on the safety set.

2.4.1 Study treatment / compliance

The duration of exposure to study treatment and duration of study will be summarized by treatment group. In addition, the number of subjects with exposure of at least certain thresholds (eg, any exposure, ≥ 1 week, ≥ 2 weeks, ≥ 4 weeks, ≥ 8 weeks, etc.) will be displayed.

Duration of exposure is defined as last dose of study treatment – first dose of study treatment + 1.

Duration of study is defined as last study visit – first dose of study treatment + 1.

The start date and end date of study treatment will be collected on eCRF and will be used to calculate the duration of exposure. In addition, the study treatment taken on each day (morning/evening) will be also be entered in the eDiary and will be listed.

2.4.2 Prior, concomitant and post therapies

Prior urticaria related medication will be summarized by type of therapy and preferred term.

Prior non-urticaria related medication will be summarized by Anatomical Therapeutic Chemical (ATC) code and preferred term for each treatment group.

Background medications will be summarized by Anatomical Therapeutic Chemical (ATC) code, preferred term and dose per administration for each treatment group.

Rescue medications will be summarized by Anatomical Therapeutic Chemical (ATC) code, preferred term and dose per administration for each treatment group.

Concomitant medications other than background or rescue medications will be summarized by Anatomical Therapeutic Chemical (ATC) code and preferred term for each treatment group.

Prior and concomitant significant surgeries and medical procedures will be summarized by primary system organ class and MedDRA preferred term for each treatment group.

Prior medications are defined as treatment taken and stopped prior to first dose of study treatment; Concomitant medications are defined as any medication given at least once between the day of first dose of randomized study treatment and the date of the last study visit.

Medications will be identified using the Novartis Drug and Therapy Dictionary (NovDTD) including the Anatomical Therapeutic Chemical (ATC) code. Medications will be presented in alphabetical order, by ATC code.

2.5 Analysis of the primary objective

All analyses for efficacy data will be based on the FAS.

The primary objective of this study is to determine a dose response signal and characterize the dose-response relationship in either LOU064 q.d. and b.i.d. doses (10 mg, 35 mg, 100 mg q.d. and 10 mg, 25 mg, 100 mg b.i.d.) compared to placebo with respect to the change from baseline in UAS7 at Week 4, and to select an appropriate dose(s) to use in Phase 3 studies.

2.5.1 Primary endpoint

[figure not shown]
The primary variable for the study is the change from baseline in UAS7 at Week 4. The UAS7 is the sum of the average daily UAS over 7 days (range from 0 to 42). Note that the weekly score is derived according to the analysis week defined in [Table 2-1](#) and [Table 2-2](#).

[figure not shown]
If one of the morning or evening score for HSS and ISS is missing, then the non-missing score for that day (morning or evening) will be used as the daily score. If one or more of the daily scores are missing, then the following principles will be applied to handle the missing data:

- The weekly Urticaria Activity Score is the sum of both the HSS7 score and the ISS7 score and will be missing if at least one of them is missing.

- If a patient has at least 4 non-missing daily scores within the 7 days, then the weekly score for HSS or ISS will be calculated as the sum of the available eDiary scores of that week, divided by the number of non-missing days multiplied by 7.
- If there are less than 4 non-missing daily scores within the 7 days, then the weekly score for HSS or ISS will be missing for that week. Accordingly, no UAS7 can be calculated.

2.5.2 Statistical hypothesis, model, and method of analysis

2.5.3 Handling of missing values/censoring/discontinuations

Subjects who discontinue from study treatment early will be encouraged to stay in the study and complete all the scheduled measurements. All the available data collected will be used for the primary analysis no matter if they took rescue medication or prohibited medication (Treatment policy).

2.5.4 Supportive analyses

Considering the primary efficacy endpoint is UAS7 score at week 4, the missing data rate is expected to be approximately 5%. So no supportive analyses is planned for the primary efficacy analysis.

2.6 Analysis of the Secondary objective

All analyses for secondary efficacy data will be based on the FAS.

Summary tables will be presented by treatment group and visit (as applicable) using descriptive statistics, which include absolute and relative frequencies for categorical variables and arithmetic mean, standard deviation, minimum, maximum, median and first and third quartile for continuous variables.

2.6.1 Secondary endpoint

UAS7 over time

Mean estimation and standard error for absolute value, change, and percent change from baseline in UAS7 score will be presented by treatment group and visit for entire study period

Summary statistics of the absolute value, change, and percent change from baseline in UAS7 will be presented by treatment group and visit for entire study period.

Summary statistics of the absolute value, change, and percent change from baseline in HSS7 will be presented by treatment group and visit for entire study period.

Summary statistics of the absolute value, change, and percent change from baseline in ISS7 will be presented by treatment group and visit for entire study period.

Complete clinical response (UAS7 = 0)

The complete clinical response, i.e. absence of hives and itch, is defined as subjects achieving UAS7= 0.

The number of subjects with UAS7= 0 will be summarized by treatment group and visit for entire study period.

Controlled disease (UAS7≤ 6)

The number of subjects with UAS7≤ 6 will be summarized by treatment group and visit for entire study period.

Absence of angioedema (AAS7= 0)

The cumulative number of weeks with an AAS7= 0 response between baseline and Week 12 will be summarized by treatment group.

Summary statistics on AAS7 weekly score will be presented by visit and treatment group.

DLQI

Seven scores will be derived from the DLQI: the score of each of the six dimensions as well as the total score of the DLQI will be calculated based on the developers' rules.

For the DLQI subscale and total score derivation, if there is only one missing score per visit, then it will be imputed to 0 and then the subscale including this item and the total score will be calculated accordingly. If there are two or more missing scores per visit, then the score will be missing.

Summary statistics will be calculated for the absolute values as well as for the change and percentage change for DLQI total score broken down by visit and treatment group.

Summary tables of the number of subjects with DLQI score of 0 or 1 will be presented by treatment group and visit for entire study period.

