1.1 Background

Chronic Spontaneous Urticaria (CSU) is defined as the spontaneous occurrence of itchy wheals (hives), angioedema or both lasting for at least 6 weeks ([Zuberbier et al 2018](#)). The classic description of urticaria is a wheal and flare with a pale elevated lesion and surrounding erythema, ranging in size from a few millimeters to a few centimeters across, usually occurring in groups and often coalescing to form large confluent lesions. CSU can be debilitating and is associated with intense itching and has a major impact on patient's well-being, suggested to be comparable to that of severe coronary artery disease ([Greaves 2003](#)). The symptoms of urticaria and urticarial-associated angioedema adversely affect daily activities and sleep ([O'Donnell et al 1997](#)). The burden of CSU on health-related quality of life (HRQoL) and work productivity is substantial ([Maurer et al 2017](#)).

Second generation H1-antihistamines are recommended as first line treatment for subjects with CSU but less than 40% of these subjects respond adequately ([Guillén-Aguinaga et al 2016](#)). While uptitration of second generation antihistamines is recommended by most CSU treatment guidelines as second line therapy ([Zuberbier et al 2018](#)), the efficacy of uptitrated H1-antihistamines in CSU has not been studied in larger clinical studies and hence uptitration is considered off-label. Omalizumab is a highly effective third line therapy for CSU subjects. However, less than 50% of subjects treated with Omalizumab reach a complete control of signs and symptoms of CSU ([Kaplan et al 2016](#)). Therefore, there is a high medical need for new treatment options for CSU subjects.

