5.1 Inclusion criteria

Subjects eligible for inclusion in this study must meet **all** of the following criteria:

1. Signed informed consent must be obtained prior to participation in the study
2. Male and female adult subjects aged ≥ 18 years of age
3. CSU diagnosis for ≥ 6 months prior to screening
4. Diagnosis of CSU inadequately controlled by second generation H1-antihistamines at the time of randomization as defined in the following:
 - The presence of itch and hives for ≥ 6 consecutive weeks prior to screening in spite of use of non-sedating H1-antihistamines according to local treatment guidelines during this time period
 - UAS7 score (range 0-42) ≥ 16 and HSS7 score (range 0-21) ≥ 8 during 7 days prior to randomization (Day 1)
5. Presence of hives must have been documented within three months before randomization (either at screening and/or at randomization; or documented in the subject's medical history)
6. Willing and able to complete an Urticaria Participant Daily eDiary (UPDD) for the duration of the study and adhere to the study protocol
7. Subjects must not have had any missing eDiary entries in the 7 days prior to randomization (Day 1)

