6.3.2 Treatment assignment, randomization

At Day 1, all eligible subjects will be randomized via Interactive Response Technology (IRT) to one of the treatment arms. The investigator or his/her delegate will contact the IRT after confirming that the subject fulfills all the inclusion/exclusion criteria. The IRT will assign a

randomization number to the subject, which will be used to link the subject to a treatment arm and will specify a unique medication number for the first package of study treatment to be dispensed to the subject.

The randomization numbers will be generated using the following procedure to ensure that treatment assignment is unbiased and concealed from subjects and investigator staff. A subject randomization list will be produced by the IRT provider using a validated system that automates the random assignment of subject numbers to randomization numbers. These randomization numbers are linked to the different treatment arms, which in turn are linked to medication numbers. A separate medication list will be produced by or under the responsibility of Novartis Global Clinical Supply using a validated system that automates the random assignment of medication numbers to packs containing the study treatment.

Randomization will be stratified by geographical region and prior usage of anti-IgE biologics (including omalizumab and ligelizumab) for treatment of CSU.

The randomization scheme for subjects will be reviewed and approved by a member of the Randomization Office.

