2.2 Analysis sets

The following analysis sets will be used for the data analysis, details refer to [section 5.5](#).

The **Randomized Set** will consist of all randomized subjects, regardless of whether or not they actually received study medication. Subjects will be analyzed according to the treatment assigned to at randomization.

The **Full Analysis Set (FAS)** will consist of all randomized subjects. Following the intent-to-treat principle, subjects will be analyzed according to the treatment and strata assigned to at randomization. Mis-randomized subjects (mis-randomized in IRT) will be excluded.

Mis-randomized subjects are defined as cases where IRT contacts were made by the site either prematurely or inappropriately prior to confirmation of the subject's final randomization eligibility and no study medication was administered to the subject.

The **Safety Set** will consist of all subjects who received at least one dose of study medication whether or not being randomized. Subjects will be analyzed according to treatment received.

If a subject has received the wrong treatment during more than 50% of the time of the entire treatment period, the treatment received will be set to this wrong treatment; otherwise it will be set to the original assigned treatment. Except for patients assigned to placebo arm, they will be summarized under LOU064 in case they took LOU064 during the treatment period independent of the time on LOU064.

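### AAS7=0 weeks are compared in all randomized subjects, including those with no angioedema at baseline: a valid contrast, but one that understates the effect in patients with active angioedema and is less sensitive to it

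*SAP*

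**What the plan says.** A secondary objective is the effect of LOU064 on angioedema, measured as the number of weeks with AAS7=0 up to Week 12 (protocol Table 2-1, SAP Table 1-1).

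- **Endpoint.** SAP 2.6.1: "The cumulative number of weeks with an AAS7= 0 response between baseline and Week 12 will be summarized by treatment group". SAP 2.6.2 adds unadjusted comparisons of each dose with placebo.
- **Population.** SAP 2.6: "All analyses for secondary efficacy data will be based on the FAS". SAP 2.2 says the FAS "will consist of all randomized subjects. Following the intent-to-treat principle", leaving out only mis-randomized subjects.
- **Entry.** Protocol 5.1 sets disease activity by itch and hives: "UAS7 score (range 0-42) ≥ 16 and HSS7 score (range 0-21) ≥ 8 during 7 days prior to randomization (Day 1"). None of the seven inclusion criteria mentions angioedema. Protocol 1.1 defines the disease as the "spontaneous occurrence of itchy wheals (hives), angioedema or both lasting for at least 6 weeks".
- **Baseline status.** SAP 2.3.2 lists "Baseline AAS7 = 0 response (Yes, No") and "Previous experience of Angioedema (Yes, No") among the baseline categories. In the readable text both serve only the baseline table.
- **Stratification.** Protocol 6.3.2: "Randomization will be stratified by geographical region and prior usage of anti-IgE biologics". Angioedema is not a factor.
- **Missing weeks.** Protocol 12.5.1 counts a week with missing AAS7 as a non-response.
- **Not visible.** The subgroup list (SAP 2.2.1) and the model specification are blacked out. The SAP document history shows only that a negative binomial analysis with an offset is planned.

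**The concern.** The count cannot exceed 12 weeks. A subject who never has angioedema and keeps a complete diary scores 12 in any arm, and no treatment can raise that score. Pooling such subjects with those who can improve has two effects. It shrinks the mean difference in proportion to the share with active angioedema. It also adds variance, because the two groups sit at different levels.

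The study is meant to select a Phase 3 regimen. At stake is that a small or unclear all-subject difference might be read as little effect on angioedema, when it partly reflects how few subjects had the symptom. The all-subject figure also does not tell a clinician how large the effect is in patients who have angioedema.

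**Working it through.** **Nothing to reproduce.** The documents give no angioedema share, SD, placebo mean, effect or power for this endpoint. What follows is illustrative.

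**Inputs from the documents.** 44 per arm (protocol 5). One-sided 5% level (SAP 2.1). Twelve weekly windows after baseline (SAP Tables 2-1 and 2-2). Baseline is Day -7 to Day -1 (SAP 2.1.1.4 and Table 2-1).

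**Assumptions.** A share f = 0.3 to 0.5 has AAS7 > 0 at baseline. In those subjects the mean is 6 weeks on placebo and 8.5 on active (effect d = 2.5), SD 4.5. In the others the mean is 11.8 weeks in both arms, SD 1. A normal approximation replaces the negative binomial model.

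**Formulas.**

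- FAS difference = f × d.
- Within-group variance W = f × 4.5² + (1 − f) × 1².
- Between-group variance, by arm: placebo Bp = f(1 − f)(11.8 − 6)²; active Ba = f(1 − f)(11.8 − 8.5)².
- z in the FAS = f × d / √[(2W + Bp + Ba)/44].
- z in the subset = d / [4.5 × √(2/(44f))].
- Information ratio = (z subset / z FAS)².

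**Worked for f = 0.4.** W = 8.1 + 0.6 = 8.7. Bp = 0.24 × 33.64 = 8.074. Ba = 0.24 × 10.89 = 2.614. z FAS = 1.00/√(28.088/44) = 1.00/0.799 = 1.25. z subset = 2.5/(4.5 × √(2/17.6)) = 2.5/1.517 = 1.65.

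| f | FAS difference (weeks) | W | Bp | Ba | z FAS | Subset n per arm | z subset | Information ratio |
|---|---|---|---|---|---|---|---|---|
| 0.3 | 0.75 | 6.775 | 7.064 | 2.287 | 1.04 | 13 | 1.43 | 1.88 |
| 0.4 | 1.00 | 8.700 | 8.074 | 2.614 | 1.25 | 18 | 1.65 | 1.73 |
| 0.5 | 1.25 | 10.625 | 8.410 | 2.723 | 1.46 | 22 | 1.84 | 1.60 |

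**Power at one-sided 5%, Φ(z − 1.645).** About 0.27, 0.35 and 0.43 in the FAS, against 0.41, 0.50 and 0.58 in the subset.

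**Baseline flag as covariate in the FAS.** If the flag removed all between-group variance, z = f × d/√(2W/44) = 1.35, 1.59 and 1.80, close to the subset. A single common term would recover slightly less, because the gap between the groups differs by arm. The covariate recovers precision; the all-subject difference stays f × d.

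**Second set of assumptions.** Subjects with baseline angioedema: 6 against 9 weeks, SD 4. The others: 11.5 weeks in both arms, SD 1.

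| f | FAS difference (3.0 weeks in the subset) | Power, FAS | Power, FAS with flag | Power, subset |
|---|---|---|---|---|
| 0.7 | 2.1 | 0.81 | 0.90 | 0.90 |
| 0.5 | 1.5 | 0.62 | 0.78 | 0.80 |
| 0.3 | 0.9 | 0.40 | 0.56 | 0.61 |

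**How firm the ceiling is.** With 5%, 10% or 20% of weeks missing and counted as non-response, an angioedema-free subject is expected to score 12 × 0.95 = 11.4, 10.8 or 9.6. If subjects quiet at baseline gain e weeks from treatment, the FAS difference is f × d + (1 − f) × e. With a placebo mean of 11.8, e cannot exceed 0.2, so at f = 0.4 the difference is at most 1.00 + 0.6 × 0.2 = 1.12 weeks.

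**The case against.** Several points on the other side are sound.

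- **The FAS contrast answers the stated question.** The objective concerns subjects with CSU, analysed as randomized. Calling it diluted only says that it is not the effect in a narrower population. This stands: a reader might infer that the comparison is biased, and the documents do not support that.
- **A quiet week is not absence of disease.** Baseline is a single 7-day window. A subject with a history of angioedema may have episodes in the next 12 weeks, and preventing them is part of the effect. This stands: it would be too strong to say that subjects with AAS7=0 at baseline tell us nothing.
- **The remedy may already be there.** A reader might infer that neither a subgroup analysis nor an adjustment is planned. With SAP 2.2.1 and the model text blacked out, the documents cannot show that. Both requests must therefore be conditional.
- **The size is assumed, and easy to overstate.** Using the placebo-arm variance in both arms gives an FAS z of 0.95, 1.15 and 1.34 and a gain of 1.9 to 2.3 times. That is wrong under these assumptions: the gap between the groups is 3.3 weeks on active, not 5.8. Even the subset z falls short of 1.645 at f = 0.3 and only just reaches it at f = 0.4.
- **The consequence is limited.** The endpoint is one of several secondary endpoints, compared without multiplicity adjustment in analyses that SAP 2.6.2 calls exploratory.

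What these points leave untouched is the mechanism. In the readable text, a capped count is compared in a mixed population, and the variable that separates the groups is used only descriptively.

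**Conclusion.** The point holds as a matter of sensitivity and interpretation. If a share f has active angioedema at baseline and the drug does little to AAS7=0 weeks in the rest, the FAS difference is about f times the effect in those patients. Under the first set of assumptions, analysing the subset carries 1.6 to 1.9 times the information of the unadjusted FAS comparison for f between 0.5 and 0.3, despite fewer subjects. The second set points the same way.

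The true share, SDs and effect are unknown from the documents. The gain would be smaller if quiet-baseline subjects often had later episodes that treatment prevented. Type I error and the primary UAS7 dose-response analysis are not affected. This is an optional-to-moderate improvement to an exploratory secondary endpoint.

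**What to change.** Keep the FAS summary and comparisons as they are. Then, unless the blacked-out subgroup list (SAP 2.2.1) or model text already provides for it:

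1. In SAP 2.6.1 and 2.6.2, add a supplementary summary and placebo comparison of AAS7=0 weeks in subjects with baseline AAS7 > 0.
2. Include the baseline AAS7=0 flag (Yes/No) as a covariate in the FAS model.

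If both are already in the blacked-out text, the sponsor need only confirm it.

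The cost is one table and one model term from a variable the SAP already defines, with no new data. There are two downsides. The subset would hold only about 13 to 22 subjects per arm if the share is 0.3 to 0.5, so its estimates will be imprecise. It also leaves out subjects with a history of angioedema but a quiet baseline week, which is one reason why it should supplement the FAS analysis and not replace it.
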